7.4.3 Vital Signs

Descriptive statistics will be provided for vital sign data (systolic and diastolic blood pressure, heart rate, respiratory rate, body temperature, and oxygen saturation) presented as both actual values and changes from baseline for each scheduled visit.

The number and percentage of patients with the following potentially clinically significant abnormal vital signs at any post-baseline visit will be summarized:

- SBP ≥ 180 mmHg and Increase ≥ 20 mmHg from Baseline
- SBP ≤ 90 mmHg and Decrease ≥ 20 mmHg from Baseline or SBP decrease >40 mmHg from baseline
- DBP ≥ 150 mmHg and Increase ≥ 15 mmHg from Baseline
- DBP ≤ 50 mm Hg and Decrease ≥ 15 mm Hg from Baseline
- HR ≥ 120 bpm and Increase ≥ 15 bpm from Baseline
- HR ≤ 50 bpm and Decrease ≥ 15 bpm from Baseline

A listing of all vital signs will be provided by treatment and subject.

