7.3.1 Day 1 (Baseline; Study Drug Infusion 1)

The day on which the subject receives their first study drug infusion will be designated Day 1 (Baseline).

The following procedures will be performed **prior to initiation of the study drug infusion**; see Schedule of Events ([Appendix A](#)):

- Review and record medical conditions.
- Review and record concomitant medications.
- Obtain subject weight
- Collect blood (serum and plasma) and urine samples for BKV testing, pharmacokinetics, immunogenicity, hematology, clinical chemistry, and urinalysis for analysis at central laboratories.
- Females of childbearing potential must have a negative urine or serum pregnancy test result within 96 hours prior to Baseline. If applicable, perform urine or serum pregnancy test.
- Record vital signs, including temperature, blood pressure, heart rate, respiratory rate, and oxygen saturation within 30 minutes prior to the initiation of the infusion.
- Perform electrocardiogram (12-lead).

The following procedures will be performed **after the initiation of the study drug infusion**; see Schedule of Events ([Appendix A](#)):

- Record vital signs, including temperature, blood pressure, heart rate, respiratory rate, and oxygen saturation approximately every 30 minutes (+/- 10 minutes) after the start of the infusion until at least 2 hours after completing the infusion. Vital signs may also be collected at any time during or after the infusion at the Investigator's discretion.
- Collect blood (serum) for pharmacokinetics within 30 minutes following the completion of the infusion and again within 3 to 6 hours after the end of the infusion.
- Review and record adverse events.
- Review and record any new concomitant medications.

It is expected that the clinical site will have adequate facilities at the location of the study drug infusions to effectively manage and treat infusion reactions.

If a subject has experienced an infusion reaction following an infusion of study drug, the Investigator should discontinue the infusion. If symptoms resolve promptly the infusion may be resumed at a slower rate. In this case, the Investigator is encouraged to continue the subject's participation in the study. If the subject continues in the study, future infusions should be administered at a slower rate and preceded by use of premedication.

Cohort 1: Study Drug Administration Day 1

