8.5.3 Vital Signs

Vital signs will include temperature, blood pressure, heart rate, respiratory rate, and oxygen saturation.

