Infusion related reaction	Mild transient reaction; interruption not indicated; intervention not indicated	Therapy or infusion interruption indicated but responds promptly to symptomatic treatment (e.g., antihistamines, NSAIDS, narcotics, IV fluids); prophylactic medications indicated for <=24 hrs	Prolonged (e.g. not rapidly responsive to symptomatic medication and/or brief interruption f infusion); recurrence of symptoms following initial improvement; hospitalization indicated for clinical sequelae	Life-threatening consequences; urgent intervention indicated	Death

Definition: A disorder characterized by adverse reaction to the infusion of pharmacological or biological substances.

CYTOKINE RELEASE SYNDROME:

Injury, poisoning and procedural complications					
CTCAE Term	Grade 1	Grade 2	Grade 3	Grade 4	Grade 5
Cytokine release syndrome	Fever with or without constitutional symptoms	Hypotension responding to fluids; hypoxia responding to <40% O ₂	Hypotension managed with one pressor; hypoxia requiring >40% O ₂	Life-threatening consequences: urgent intervention indicated	Death

Definition: disorder characterized by fever, tachypnea, headache, tachycardia, hypotension, rash, and/or hypoxia caused by the release of cytokines.

Navigational Note: Also consider reporting other organ dysfunctions including neurological toxicities such as: Psychiatric disorders: Hallucinations or Confusion; Nervous system disorders: Seizure, Dysphasia, Tremor, or Headache.

SERUM SICKNESS:

Injury, poisoning and procedural complications					
CTCAE Term	Grade 1	Grade 2	Grade 3	Grade 4	Grade 5
Serum sickness	Asymptomatic; clinical or diagnostic observations only; intervention not indicated	Moderate arthralgia: fever, rash, urticaria, antihistamines indicated	Sever arthralgia or arthritis; extensive rash; steroids or IV fluids indicated	Live-threatening consequences; pressor or ventilatory support indicated	Death

Definition: A disorder characterized by a delayed-type hypersensitivity reaction to foreign proteins derived from an animal serum. It occurs approximately six to twenty-one days following the administration of the foreign antigen. Symptoms include fever, arthralgias, myalgias, skin eruptions, lymphadenopathy, chest marked discomfort and dyspnea.

Navigational Note: -

INVESTIGATIONS:

Injury, poisoning and procedural complications					
CTCAE Term	Grade 1	Grade 2	Grade 3	Grade 4	Grade 5

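### SAP 7.4.3 counts threshold abnormalities only for blood pressure and heart rate; a measured fever, desaturation or tachypnea enters an incidence by arm only if it is reported as an adverse event or infusion reaction

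*SAP*

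**What the plan says.** Protocol 8.5.3 defines the set: "Vital signs will include temperature, blood pressure, heart rate, respiratory rate, and oxygen saturation". On infusion days (Protocol 7.3.1, 7.3.5, 7.3.8 and 7.3.10, and Appendix A footnote 17) the set is taken shortly before the infusion and then "approximately every 30 minutes (+/- 10 minutes) after the start of the infusion until at least 2 hours after completing the infusion".

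SAP 7.4.3 provides three outputs:

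- Descriptive statistics for systolic and diastolic pressure, heart rate, respiratory rate, temperature and oxygen saturation, "presented as both actual values and changes from baseline for each scheduled visit". SAP 7.1.4 adds that continuous summaries show minimum and maximum.
- A count of patients with abnormal values: "The number and percentage of patients with the following potentially clinically significant abnormal vital signs at any post-baseline visit will be summarized". The list opens with "SBP ≥ 180 mmHg and Increase ≥ 20 mmHg from Baseline" and closes with "HR ≤ 50 bpm and Decrease ≥ 15 bpm from Baseline". Every row concerns systolic pressure, diastolic pressure or heart rate.
- "A listing of all vital signs will be provided by treatment and subject".

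Protocol 10.8.1 is somewhat wider. It plans summaries by visit and time, and flags abnormal values in the listing where normal ranges exist. SAP 7.4.3 repeats neither provision, and SAP Section 9 does not record a change. Under Protocol Section 10 the SAP prevails on analysis.

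**The concern.** Safety and tolerability are the primary objective. Protocol 10.4 names body temperature and oxygen saturation, with blood pressure and pulse, among the vital signs by which it is measured. Two of those four have no abnormality criterion.

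The omitted parameters bear on a named risk. Protocol 1.8 lists infusion-related reactions, including cytokine release syndrome, as potential risks. Appendix D describes that syndrome as a "disorder characterized by fever, tachypnea, headache, tachycardia, hypotension, rash, and/or hypoxia caused by the release of cytokines", with fever in its Grade 1 cell and hypoxia in its Grade 2 cell. Fever, hypoxia and tachypnea are the features of this description that correspond to the three parameters without a row.

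What is at stake is a by-arm incidence of measured abnormalities that does not depend on someone deciding to report an event. The same gap would carry into the tables and listings that the SSRC uses to assess vital signs before Cohort 3 opens (SAP 8.2 and 8.2.1).

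**Working it through.** The plan states no figure to reproduce. The check is a count of criteria, a count of readings, and a search for any other output that would tabulate the three parameters.

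**Criteria in SAP 7.4.3**

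| Parameter | Descriptive statistics | Listed | Threshold criteria |
|---|---|---|---|
| Systolic pressure | yes | yes | 2 |
| Diastolic pressure | yes | yes | 2 |
| Heart rate | yes | yes | 2 |
| Temperature | yes | yes | 0 |
| Respiratory rate | yes | yes | 0 |
| Oxygen saturation | yes | yes | 0 |

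Three of the six summarized parameters have a criterion.

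**Readings after the start of infusion, per subject and parameter.** Inputs are the minimum infusion times of 60 and 180 minutes (Protocol 5.3), 120 minutes of observation afterwards, and one reading per 30 minutes. Readings per infusion = (infusion time + 120) / 30.

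- 60-minute infusion: (60 + 120) / 30 = 6
- 180-minute infusion: (180 + 120) / 30 = 10
- Cohort 1, four 60-minute infusions: 4 × 6 = 24
- Cohort 2, one 180-minute and three 60-minute infusions: 10 + 3 × 6 = 28
- Cohort 3, four 180-minute infusions: 4 × 10 = 40

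These are approximate. They assume minimum infusion times, all four infusions given, and exact 30-minute spacing.

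**Other outputs that could count these values**

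- Adverse event tables (SAP 7.4.1): treatment-emergent events by organ class, preferred term and worst grade, and an overview row for infusion reactions. A fever or desaturation is included once it has been reported.
- Route into those tables (Protocol 9.1): an abnormal finding becomes an adverse event if it needs intervention, leads to action with study drug, or is judged reportable by the investigator. The infusion-associated eCRF in Protocol 9.1.4 covers the infusion and the 2 hours after it, but is completed only once an adverse event has been recognized.
- Vital-sign listing (SAP 7.4.3): shows every value but gives no incidence. The SAP states flagging for laboratory values (7.4.2) and not for vital signs.

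No other planned output in either document tabulates temperature, respiratory rate or oxygen saturation against a threshold.

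**Which readings enter.** SAP 7.1.3 takes baseline as the last value before the first dose. The readings during and after the Day 1 infusion therefore follow baseline in time but belong to the visit named Baseline. The abnormality count is framed in terms of visits after baseline, and the SAP does not say whether these Day 1 readings fall inside it. Nor does it say which of the repeated infusion-day readings enters the visit summary.

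**The case against.** The strongest case on the other side is that the plan already catches what matters, and much of that case stands.

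A reader might infer that fever or hypoxia is not counted at all. The documents do not support this. An episode judged clinically significant is to be reported as an adverse event, is tabulated by arm, and goes on a dedicated form if it is associated with the infusion and occurs during it or within 2 hours after it.

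A reader might also infer that visit-level statistics are the only output, or that a brief spike would be lost in an arm mean. Neither follows. All vital signs are listed, and minimum and maximum are shown, so an extreme value among the summarized readings appears undiluted. The SAP also does not say that readings within a visit are averaged.

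Nor do the documents say why the 30-minute readings are taken. Linking them to cytokine release and infusion reactions is a reasonable inference from Protocol 1.8, the discontinuation rules in 3.3.2 and Appendix D, but it is an inference. The existing low-systolic and high-heart-rate rows already address the hypotension and tachycardia components of the syndrome.

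Finally, active arms have about 8 subjects each, the SSRC receives unblinded individual profiles at both interim reviews, and the DSMB sees cumulative unblinded safety data. At this size, individual abnormalities can be found by reading, and no rule in the documents requires a threshold for every vital sign.

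What remains is narrower. Adverse event reporting rests largely on investigator judgment, so it does not replace a count of measured values. The SAP accepts this elsewhere: it counts blood pressure, heart rate and liver-test abnormalities by threshold although these too can be reported as adverse events. It gives no reason for leaving out the other three vital signs.

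**Conclusion.** The point holds as a minor gap. Three of six summarized vital-sign parameters have no abnormality criterion, two of them named in Protocol 10.4 as measures of the primary objective. For these three, none of the roughly 24, 28 or 40 post-start readings per subject is compared with a threshold. A measured abnormality that nobody reports as an adverse event or infusion reaction contributes to no incidence by arm. It can be seen only in the listing and profiles, or as a minimum or maximum if that reading enters the summary.

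This rests on the SAP list being programmed as written and on the SAP prevailing over Protocol 10.8.1. How many subjects would be affected cannot be estimated, because the documents give no rates for unreported abnormal readings. No efficacy analysis, error rate or sample size is touched.

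**What to change.** In SAP 7.4.3:

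- Add analysis criteria for temperature, oxygen saturation and respiratory rate. The sponsor sets the values and fixes them before unblinding.
- State that all readings from the start of infusion to the last post-infusion reading count, including those on Day 1.
- Report the number and percentage of subjects meeting each criterion by arm.
- List those subjects beside their reported infusion-associated adverse events, so that measured but unreported abnormalities are visible.
- Include these outputs in the second interim package.

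Because longer infusions give more readings, and so more chances to meet a criterion, show the number of readings per subject beside the counts. With 4 placebo subjects per cohort, pooled placebo averages (24 + 28 + 40) / 3 ≈ 31 readings, against 24 in the Cohort 1 active arm and 40 in the Cohort 3 active arm.

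The cost is three table rows and one listing from vital signs the protocol already collects. These are tabulation criteria only. They change no rule for stopping, slowing or managing an infusion.

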10.4 Safety Analysis

The primary objective of this study is to assess the safety and tolerability of MAU868 as measured by adverse events, vital signs (blood pressure, pulse rate, body temperature, oxygen saturation), ECG, and laboratory measurements.

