Blood prolactin abnormal	Asymptomatic; clinical or diagnostic observations only; intervention not indicated	Moderate symptoms; limiting instrumental ADLs	-	-	-

Definition: A finding based on laboratory test results that indicate abnormal levels of prolactin hormone in a blood specimen.

Navigational Note: -

CTCAE Term	Grade 1	Grade 2	Grade 3	Grade 4	Grade 5
Carbon monoxide diffusing capacity decrease	3-5 units below LLN; for follow-up, a decrease of 3-5 units (ml/min/mm Hg) below the baseline value; asymptomatic and intervention not indicated	6-8 units below LLN; for follow-up, an asymptomatic decrease of >5 – 8 units (ml/min/mm Hg) below the baseline value; symptomatic and intervention no indicated	Asymptomatic decrease of >8 units drip; >5 units drop along with the presence of pulmonary symptoms (e.g., >Grade 2 hypoxia or >Grade 2 dyspnea); intervention indicated	-	-

Definition: A finding based on lung function test results that indicate a decrease in the lung capacity to absorb carbon monoxide.

Navigational Note: Also consider Respiratory, thoracic and mediastinal disorders: Respiratory failure or Dyspnea

CTCAE Term	Grade 1	Grade 2	Grade 3	Grade 4	Grade 5
Ejection fraction decreased	-	Resting ejection fraction (EF) 50-40%; 10 -19% drop from baseline	Resting ejection (EF) 39 – 20%; >=20% drop from baseline	Resting ejection fraction (EF) < 20%	-

Definition: The percentage computed when the amount of blood effected during a ventricular contraction of the heart is compared to the amount that was present prior to the contraction.

Navigational Note: -

CTCAE Term	Grade 1	Grade 2	Grade 3	Grade 4	Grade 5
Electrocardiogram QT corrected interval prolonged	Average QTc 450 – 480 ms	Average QTc 481 – 500 ms	Average QTc >=501ms; >60 ms change from baseline	Torsade dep pointes; polymorphic ventricular tachycardia; signs/symptoms of serious arrhythmia	-

Definition: A finding of a cardiac dysrhythmia characterized by an abnormally long corrected QT interval

Navigational Note: -

CTCAE Term	Grade 1	Grade 2	Grade 3	Grade 4	Grade 5
Electrocardiogram T wave abnormal	T wave flattening	Nonspecific ST segment change	-	-	-

Definition: A disorder characterized by Electrocardiogram T wave amplitude changes.

Navigational Note: -

CTCAE Term	Grade 1	Grade 2	Grade 3	Grade 4	Grade 5

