7.4.1 Adverse Events (AEs)

AEs will be captured from the date of informed consent through study completion. All AEs will be coded to system organ class and preferred term using the MedDRA, Version 22.1. Treatment-emergent adverse events (TEAEs) are defined as AEs that start on or after the administration of study drug.

An overview of AEs will be provided including counts and percentages of subjects (and event counts) with the following:

- Any AEs;
- Any infusion reactions;
- Any TEAEs (overall and by maximum severity);
- Any study drug-related TEAEs (overall and by maximum severity);
- Any TEAEs leading to discontinuation of study drug;
- Any TEAEs leading to discontinuation of the study;
- Any serious AEs (SAEs) (overall and by maximum severity);
- Any treatment-emergent SAEs (TESAEs);
- Any study drug-related treatment-emergent SAEs (TESAEs);
- Any death.

The number and percentage of subjects who experienced at least one TEAE will be presented by system organ class and preferred term. Drug-related TEAEs, study drug withdrawals due to TEAEs, study discontinuation due to TEAEs, and all SAEs will be summarized in the same manner.

Summaries will be provided by worst grade for the number and percentage of subjects with TEAEs and for subjects with drug-related TEAEs by system organ class and preferred term.

Although a subject may have two or more TEAEs, the subject is counted only once within a system organ class and preferred term category. The same subject may contribute to two or more preferred terms in the same system organ class category.

A list of patients who have SAEs, a list of patients who discontinue from study drug due to TEAEs, and a list of death due to AEs will be provided. All adverse events will be listed.

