7.4.2 Clinical Laboratory Tests

Central laboratory test results (chemistry, hematology, coagulation, and urinalysis) at each scheduled visit and change from baseline will be summarized with descriptive statistics. See Appendix A for a complete list of clinical laboratory analytes.

Shift tables from baseline to each scheduled post-baseline visit will be provided for selected chemistry parameters (ALT, AST, ALP, Total Bilirubin, Creatinine, Creatinine Kinase, Sodium, Potassium, Bicarbonate, Calcium, and Phosphorus) and hematology parameters (Hematocrit, Hemoglobin, Platelets, White blood cell count and differential). For chemistry parameters, the following categories will be used: < the lower limit of normal (LLN), normal, >ULN to $\leq 2 \times$ ULN, $>2 \times$ ULN to $\leq 3 \times$ ULN, $>3 \times$ ULN to $\leq 5 \times$ ULN, $>5 \times$ ULN, and missing. For hematology parameters, the following categories will be used: low, normal, high, and missing.

The number and percentage of patients with the following potentially clinically significant abnormal liver function tests at any post-baseline visit will be summarized:

- ALT $\geq 3 \times$ ULN
- ALT $\geq 5 \times$ ULN
- ALT $\geq 10 \times$ ULN
- AST $\geq 3 \times$ ULN
- AST $\geq 5 \times$ ULN
- AST $\geq 10 \times$ ULN
- ALT or AST $\geq 3 \times$ ULN
- Total Bilirubin $>1.5 \times$ ULN
- Total Bilirubin $>2 \times$ ULN
- ALT or AST $\geq 3 \times$ ULN and Total Bilirubin $>1.5 \times$ ULN
- ALT or AST $\geq 3 \times$ ULN and Total Bilirubin $>2 \times$ ULN
- Potential Hy's Law cases: ALT or AST $\geq 3 \times$ ULN and Total Bilirubin $>2 \times$ ULN, and ALP $\leq 2 \times$ ULN

A listing of subjects with any post-baseline clinically significant abnormal liver function tests will be presented.

All clinical laboratory data will be listed. Values outside the normal ranges will be flagged.

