7.4.4 Electrocardiograms

Descriptive statistics will be provided by treatment for 12-lead ECG interval data (Heart rate, PR interval, QRS duration, QT interval, and RR interval) and changes from baseline for each scheduled visit. The ECG overall interpretation categories (Normal, Abnormal not clinically significant, and Abnormal clinically significant) will be summarized by visit.

All ECG measurements and the overall interpretation will be listed by treatment and subject.

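### Three SAP safety summaries (high diastolic pressure, QT, electrolyte shifts) are poorly matched to what they should detect, so categorical and severity-graded detection is lost for the primary objective

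*SAP*

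**What the plan says.** Protocol 10.4 sets the context: "The primary objective of this study is to assess the safety and tolerability of MAU868 as measured by adverse events, vital signs", ECG and laboratory measurements.

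- **Vital signs (SAP 7.4.3).** The potentially clinically significant categories include a systolic row at or above "180 mmHg and Increase" of at least 20 mmHg, and a diastolic row at or above "150 mmHg and Increase" of at least 15 mmHg. There is no other categorical rule for high diastolic pressure. The low rows use 90 mmHg systolic and 50 mmHg diastolic. Descriptive statistics by visit are also planned, and "A listing of all vital signs will be provided by treatment and subject".
- **Laboratory (SAP 7.4.2).** Shift tables cover liver tests, creatinine and CK together with sodium, potassium, bicarbonate, calcium and phosphorus. One scale applies to all of them. The sentence beginning "For chemistry parameters, the following categories will be used" gives one class below LLN, normal, then classes bounded at ULN, 2x, 3x and 5x ULN.
- **ECG (SAP 7.4.4).** Descriptive statistics are planned for "12-lead ECG interval data (Heart rate, PR interval, QRS duration, QT interval, and RR interval"; the list ends there. No corrected QT and no outlier categories are planned. Protocol Appendix D grades "Electrocardiogram QT corrected interval prolonged": 450–480 ms, 481–500 ms, and then Grade 3 at ≥501 ms or a change of >60 ms from baseline.
- **Adverse events (SAP 7.4.1).** TEAEs "are defined as AEs that start on or after the administration of study drug"; worsening is not mentioned.

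**The concern.** A categorical safety table is there to pick out the individual patient whom a mean would hide. That matters here, with about 8 subjects per active group and 12 combined placebo subjects (SAP 3). A row whose threshold almost nobody can reach reads as zero in every arm and looks like reassurance. A shift table that puts a slightly raised potassium and a dangerous one in the same cell cannot show severity. A QT summary without rate correction does not use the quantity that the protocol itself grades. All three outputs serve the primary objective, and all three can be corrected from data already collected.

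**Working it through.** The SAP gives no derivation for these cut-offs, so there is no plan figure to reproduce. The check compares the rules with each other and with Appendix D.

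**(a) Diastolic flag.** Inputs are from SAP 7.4.3.
- Pulse pressure at the two high limits: 180 − 150 = 30 mmHg. At the two low limits: 90 − 50 = 40 mmHg.
- A diastolic of 150 is more plausible at a much higher systolic (at 200 mmHg the pulse pressure is 200 − 150 = 50), but by then the systolic limit has long been passed.
- A diastolic of 110–149 with systolic below 180 meets neither high limit. For example, a diastolic of 130 after a rise of 50 goes unflagged unless systolic also reaches 180 with a rise of at least 20.

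**(b) QT.** RR = 60/HR in seconds; QTcF = QT/RR^(1/3); QTcB = QT/RR^(1/2). The heart rates and QT values are illustrations, not data from the documents.
- QT 360 ms at 60 bpm: RR = 1.0, QTcF = 360 ms.
- QT 360 ms at 100 bpm: RR = 0.6, 0.6^(1/3) = 0.843, QTcF = 360/0.843 = 427 ms.
- The QT change is 0 and the QTcF change is 427 − 360 = 67 ms, above the 60 ms change listed under Grade 3.
- The formula matters. With QT constant at 400 ms and heart rate going from 70 to 100 bpm, QTcF goes from 421 to 474 (+53 ms) and QTcB from 432 to 516 (+84 ms). Bazett meets the Grade 3 criteria and Fridericia does not. Appendix D names no formula, so the SAP must.
- A rate difference between visits is plausible by design: the Day 1 ECG is taken before dosing and the Day 84 ECG after dosing (Protocol Appendix A, note 18).

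**(c) Electrolytes.** The documents give no ULNs, so these ranges are assumptions.

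| Analyte | Assumed ULN | 2x ULN |
|---|---|---|
| Sodium, mmol/L | 144–148 | 288–296 |
| Potassium, mmol/L | 5.0–5.5 | 10.0–11.0 |
| Bicarbonate, mmol/L | 28–32 | 56–64 |
| Calcium, mg/dL | 10.2–10.6 | 20.4–21.2 |
| Phosphorus, mg/dL | 4.5–4.7 | 9.0–9.4 |

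For the first four, essentially every high value falls between ULN and 2x ULN, and the three classes above stay empty. All low values share one class. Phosphorus could exceed 2x ULN, so the point is not made for it.

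**(d) TEAE definition (minor).** AEs are captured from consent, and screening lasts up to 10 days. Protocol 9.1 requires worsening of a condition present at baseline, or significant worsening of a laboratory or ECG finding present at initial dosing, to be reported as an AE. Such a record would normally carry a post-dose onset and count as a TEAE. The gap is an AE that starts in screening, worsens after dosing and keeps its screening onset date. Neither document says which date is recorded.

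**The case against.** The strongest reply is that little is hidden.

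- SAP 7.1.4 gives minimum and maximum by treatment group, and SAP 7.4.2 and 7.4.3 apply descriptive statistics to values and changes at each scheduled visit. With about 8 subjects per active group, an extreme diastolic or potassium value at a scheduled visit would show as the maximum, unless a worse value did.
- All vital signs, laboratory values and ECG measurements are listed, and out-of-range laboratory values are flagged. Clinically significant ECG abnormalities are tabulated by visit, and graded AEs are tabulated by worst grade.
- The SSRC sees unblinded patient profiles and the DSMB sees cumulative unblinded safety data.
- Appendix D is a generic CTCAE extract, and Protocol 1.8 does not name QT prolongation as a potential risk.
- Discontinuation under Protocol 3.3.2 turns on treatment-related grades and clinical significance, not on SAP tables.

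All of this stands, and it limits the point. A reader might infer that these tables would show no signal in diastolic pressure, potassium or QTc whether or not one existed; the outputs just listed rule that out. A reader might also infer that the TEAE definition ignores worsening altogether. Protocol 9.1 largely covers it, SAP 7.1.5 treats unresolved partial dates as treatment-emergent, and a missed event would still be among all AEs, in the listing and, if serious, in the SAE tables.

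The reply does not justify a diastolic row that almost no one can enter, shift classes that stay empty, or the absence of the interval that the protocol grades.

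**Conclusion.** The point holds in limited form. Three summaries serving the primary objective lose categorical or severity-graded detection; they do not lose all signal. The diastolic row would read about 0% in every arm. The upper three shift classes would be empty for four electrolytes. A QTc change such as the 67 ms in the example would have to be worked out from listings. The TEAE gap is narrow.

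The electrolyte limb rests on the assumed ULNs and on the judgement that values above twice ULN practically do not occur for those four analytes. The diastolic limb rests on the judgement that a diastolic of 150 mmHg is very rare.

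A reader might infer that 150 is a transposition of 105. Nothing in either document shows what value was intended, so the entry should be treated as one to verify. No sample size, alpha or power figure is affected, and neither is any rule for managing subjects.

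**What to change.** - **SAP 7.4.3:** the sponsor checks the diastolic limit and replaces it with a reachable, justified cut-off for this table.
- **SAP 7.4.4:** derive QTcF per ECG from the QT and RR already collected, and name the formula. Summarise values, change from baseline and the Appendix D categories (450–480, 481–500, ≥501 ms, and >60 ms change).
- **SAP 7.4.2:** for sodium, potassium and calcium, use analyte-specific low and high grades where CTCAE v5 defines them. Appendix D does not reproduce those rows, so they must come from the full version that it points to. For bicarbonate, Appendix D lists a single low grade, so low/normal/high is enough unless the full version gives more. Keep ULN multiples for liver tests and CK.
- **SAP 7.4.1 (minor):** extend the TEAE definition to AEs that start, or worsen in grade, on or after the first dose.

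The cost is SAP wording and table shells, with no new data collection. SAP section 1 has the plan finalised before database lock, so the changes belong before that point.
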